# 9.3.3. Mediation

### Table 3.Mediation Variables

Variable	Role	Operational definition	Measurement period
Community-acquired pneumonia (CAP)	Mediator	
 
≥1 ICD-9-CM or ICD-10-CM diagnosis code for CAP in any setting, where there were no hospital admissions or ventilator use within the 30 days prior.
 
CAP with be categorized as having 0 or ≥1 CAP event. Individuals will be classified as having ≥1 CAP event if there is at least one diagnosis code for CAP during one of the following time segments:
 
1. ≥0 days after the unvaccinated index date and before the minimum date of censoring for the unvaccinated time segment
 
2. ≥14 days after the vaccinated index date and before the minimum date of censoring for the vaccinated time segment.
 
ICD-9-CM and ICD-10-CM codes are listed in Annex 1.
 
	Follow-up
Community-acquired pneumonia (CAP) sensitivity	Mediator	
 
≥1 ICD-9-CM or ICD-10-CM diagnosis code for CAP in the hospital setting, where there were no hospitalizations or ventilator use in the 30 days prior the hospital admission associated with the CAP diagnosis.
 
For individuals with multiple CAP diagnosis codes during the 1-year follow-up period, CAP will be classified as the highest level of care associated with a CAP diagnosis code.
 
CAP with be categorized as having 0 or ≥1 CAP event. Individuals will be classified as having ≥1 CAP event if there is at least one diagnosis code for
 
	Follow-up

PFIZER CONFIDENTIAL

CT24-WI-GL02-RF02 6.0 Non-Interventional Study Protocol Template For Secondary Data Collection Study Page 25 of 53

CAP during one of the following time segments:

 
≥0 days after the unvaccinated index date and before the minimum date of censoring for the unvaccinated time segment
 

 
4. ≥14 days after the vaccinated index date and before the minimum date of censoring for the vaccinated time segment.
 

ICD-9-CM and ICD-10-CM codes are listed in Annex 1.

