### **Primary Outcome Analysis**

The weighted cumulative incidence function (CIF) will be estimated to describe and account for mortality as a competing risk of MACE. This approach provides a non-parametric estimate of the cumulative incidence function, accounting for the competing risk events. The crude weighted CIF will be presented with the log-rank test to compare the CIF curve between the PCV13 vaccinated and PCV13 unvaccinated cohorts.

A cause-specific Cox proportional hazards model with a time-varying covariate for influenza vaccination status and a time-segment approach to PCV13 vaccination status will be used for the primary analysis. The cause-specific cox model will be used to estimate hazard ratios (HRs) for the first event of each MACE outcome, comparing PCV13 vaccinated with PCV13 unvaccinated Medicare beneficiaries. The model accounts for the possibility of competing risks by focusing on the cause-specific hazard. A time segment approach will be used to account for changes in PCV13 exposure status during follow-up, allowing adults who receive PCV13 during the study period to contribute a PCV13 unvaccinated and a PCV13 vaccinated time segment to the study.

For the any MACE outcome model, individuals are censored after experiencing their first MACE event during a given time segment, irrespective of whether the MACE event is myocardial infarction, stroke, or heart failure. The remaining models examine each type of MACE separately and experiencing one type of MACE event (i.e., myocardial infarction) is not a censoring criterion for the other types of MACE outcomes (i.e., stroke or heart failure) during a given time segment.

The HR for PCV13, with a 95% confidence interval, will be calculated over the follow-up period. If the proportional hazards assumption is violated—indicating the effect of PCV13 on the risk of MACE events changes over time—HRs will be estimated for specific follow-up periods (i.e., 0-1 years and 0-3 years).

[figure not shown]

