### **Mediation** Analysis

The study will also include a secondary analysis to examine mediation. The mediation analysis will estimate the direct and indirect effects of PCV13 receipt on MACE, examining the extent to which the relationship between PCV13 and MACE within 1 year of follow-up is mediated by CAP. Direct (c') and indirect effects (a\*b) will be estimated. This analysis will employ the product method, which

PFIZER CONFIDENTIAL

CT24-WI-GL02-RF02 6.0 Non-Interventional Study Protocol Template For Secondary Data Collection Study Page 36 of 53 uses a logistic weighted mediation model to assess the mediator and a Cox model weighted outcome model to derive the HR and confidence intervals. Additionally, a counterfactual-based mediation analysis may be considered. This approach utilizes simulations to estimate the Controlled Direct Effect (CDE) and the Natural Indirect Effect (NIE), providing a comprehensive understanding of the mediation process. The mediation analysis will only adjust for influenza vaccination status during baseline. Further details on the mediation analysis will be provided in the SAP.

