## **16. ANNEX 1. LIST OF STANDALONE DOCUMENTS**

Numbe	r	Document reference number	Date	Title
1		1.0	10-Sep-2024	Diagnosis Codes (ICD-10-CM) for Identifying All-cause Pneumonia

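### Table 3 anchors the 30-day CAP screen at admission in the hospital-only row and at no stated date in the main row, so in-stay pneumonia can be scored as community-acquired and the two mediators need not be nested

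*Protocol*

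**What the plan says.** Secondary objective 4 asks how far CAP mediates the effect of PCV13 on MACE at 1 year. Section 9.7 (Mediation Analysis) describes this as "examining the extent to which the relationship between PCV13 and MACE within 1 year of follow-up is mediated by CAP" and estimates the indirect effect as the product of the vaccine-to-CAP path (a) and the CAP-to-MACE path (b).

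Table 3 in Section 9.3.3 defines the mediator twice:

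- **Main row:** a "diagnosis code for CAP in any setting, where there were no hospital admissions or ventilator use within the 30 days prior". The sentence ends there and does not say prior to what.
- **Sensitivity row:** a code in the hospital setting, "where there were no hospitalizations or ventilator use in the 30 days prior the hospital admission associated with the CAP diagnosis". The anchor here is the admission.

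In both rows a person counts as a case "if there is at least one diagnosis code for CAP during one of the following time segments", and the code must fall on or after the start of follow-up "and before the minimum date of censoring for the unvaccinated time segment", with a matching clause for vaccinated segments. Neither row refers to a present-on-admission flag, a diagnosis position or a day of stay.

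Table 3 sends the reader to Annex 1 (Section 16) for the codes. The only entry there is a standalone document titled "Diagnosis Codes (ICD-10-CM) for Identifying All-cause Pneumonia", and the codes themselves are not listed. The Abstract and Section 9.7 (Sensitivity Analysis) present the hospital-only analysis as a narrowing of the main CAP definition by setting.

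**The concern.** A general pneumonia code does not say where the infection began. Unless the code list does that work, the 30-day screen is what makes the mediator community-acquired. In the sensitivity row the screen stops at the hospital door: a patient admitted for a hip fracture who develops pneumonia a week later passes it, and so does one whose ventilation starts after admission. In the main row the result depends on a dating convention that the table does not give.

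Two things are at stake. First, pneumonia acquired in hospital may respond differently to PCV13 and may carry a different MACE risk, so mixing it in can bias the mediation estimate. Second, the sensitivity analysis is presented as changing the setting only. If the anchor changes as well, a difference between the two results has no clear meaning.

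**Working it through.** **Classification check.** The plan gives no figure on this point, so the first step is to apply the two rules to two records. Neither record has a hospital stay or ventilation in days 70 to 99.

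- Record A: admitted on day 100 for hip fracture, pneumonia arises on day 107.
- Record B: admitted on day 100 with pneumonia, its only pneumonia code being the inpatient one.

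The admission day itself is taken as not prior to itself. The discharge day D is at most 100 + 30 = 130.

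| Rule | 30-day window | A (in-stay) | B (true CAP) |
|---|---|---|---|
| Sensitivity row | days 70–99 | 1 | 1 |
| Main row, code dated on day of diagnosis | A: 77–106; B: 70–99 | 0 (window contains day 100) | 1 |
| Main row, code dated at admission | 70–99 | 1 | 1 |
| Main row, code dated at discharge | D−30 to D−1 | 0 (contains day 100) | 0 (contains day 100) |

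The sensitivity row scores A as CAP. The main row gives a different pair of results under each convention. Under diagnosis dating A is a hospital-only case but not an any-setting case; under discharge dating so are both A and B. Nesting holds for these records only under admission dating. A pneumonia code from another setting on or before day 100 would rescue B under discharge dating.

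**Role of censoring.** In the any-MACE analysis, "individuals are censored after experiencing their first MACE event during a given time segment". Pneumonia dated on or after the first MACE is therefore not counted. In-stay pneumonia dated before it still is.

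**Illustrative size.** All inputs are assumptions; none is in the protocol.

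- f = share of scored CAP among the unvaccinated that is in-stay pneumonia unaffected by PCV13: 5% to 30%
- RR = true risk ratio of PCV13 on CAP: 0.80 to 0.95
- MACE hazard ratio after CAP: 3; after in-stay pneumonia: 1.5 to 6

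Formulas:

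- Observed RR = (1 − f)·RR + f
- Path a ratio = ln(observed RR) / ln(RR)
- Observed mediator HR = (1 − f)·3 + f·HR_in-stay
- Log-scale a·b ratio = path a ratio × ln(observed HR) / ln 3
- Absolute-scale ratio = (observed HR − 1) / (3 − 1). Path a drops out because the risk difference in scored CAP, p(1 − f)(1 − RR), equals the true one, where p is the scored CAP risk among the unvaccinated.

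Example with f = 0.30, RR = 0.80, HR_in-stay = 1.5:

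- Observed RR = 0.70 × 0.80 + 0.30 = 0.86
- Path a ratio = ln 0.86 / ln 0.80 = 0.676
- Observed HR = 0.70 × 3 + 0.30 × 1.5 = 2.55
- a·b ratio = 0.676 × ln 2.55 / ln 3 = 0.576
- Absolute-scale ratio = 1.55 / 2 = 0.775

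| f | Path a, log scale | a·b, log scale | Indirect effect, absolute scale |
|---|---|---|---|
| 5% | 0.944–0.949 | 0.923–0.991 | 0.962–1.075 |
| 10% | 0.889–0.898 | 0.848–0.976 | 0.925–1.150 |
| 20% | 0.781–0.796 | 0.706–0.928 | 0.850–1.300 |
| 30% | 0.676–0.695 | 0.576–0.860 | 0.775–1.450 |

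When both kinds of pneumonia carry the same MACE hazard, the absolute-scale ratio is exactly 1. The plan models the mediator by logistic regression, so path a would be a log odds ratio; the risk-ratio form used here is close to it if CAP is uncommon.

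**The case against.** Several points on the other side are fair.

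- **The main mediator may be sound.** The admission-anchored wording belongs to the sensitivity row alone. Read as 30 days before the code, the main row excludes both in-stay and ventilator pneumonia. A reader might infer that the main mediation analysis counts hospital-acquired cases; the text supports that only if inpatient codes are dated at admission. What stands is that the anchor is not stated.
- **The code list is not visible.** A reader might infer that ventilator-specific or hospital-acquired codes are on it. The title suggests no restriction but does not prove it. The hip-fracture case needs only a general pneumonia code.
- **The mechanism is not limited to community onset.** Section 7 names a reduction in all-cause pneumonia. In-stay pneumonia is therefore not plainly off the described pathway, and if PCV13 prevents some of it the loss in path a is smaller. Objective 4 and Table 3 nevertheless say community-acquired.
- **The hospital-only analysis is given no specificity rationale.** It would be an inference to say that it was meant as the more specific one.
- **The SAP may settle it.** Section 9.7 defers mediation detail to the SAP, which is not at hand. That could supply the main row's anchor. It does not remove the rule already written in the sensitivity row, nor the different wording of the two rows.

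**Conclusion.** The point holds in a limited form. As written, the hospital-only definition scores pneumonia arising during the stay as CAP. The main definition has no stated anchor and gives three different mediators under three plausible dating conventions. Under two of those the hospital-only cases are not a subset of the any-setting cases, so the sensitivity analysis would not isolate setting.

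This can bias the estimate for secondary objective 4. On assumed contamination of 5% to 30%, with no PCV13 effect on in-stay pneumonia, the log-scale vaccine-to-CAP path falls to about 0.95 to 0.68 of its true value. That range applies to the hospital-only row. In the any-setting row contamination arises only under admission dating and then scales with the inpatient share of CAP.

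A reader might go further and conclude that the mediation result is distorted in a known direction. The documents do not support that. They give neither the contamination share nor the MACE risk after each kind of pneumonia. Over the assumed values the indirect effect falls on the log scale but may fall, rise or stay the same on the absolute scale. The primary MACE analysis and the other secondary outcome analyses do not use this variable.

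**What to change.** In both rows of Table 3:

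1. Date inpatient pneumonia at the admission date and apply the 30-day look-back for hospital stays and ventilation from that date. For outpatient codes, apply it from the service date.
2. Count an inpatient pneumonia code only if it is flagged present on admission or, where no flag is available, if it is the principal or admitting diagnosis.

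With a common anchor and a common onset rule, the hospital-only analysis becomes a true restriction of the main one.

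The cost is a sentence or two in Table 3 and a filter on claim fields. Some true CAP coded only as a secondary, unflagged diagnosis will be lost, which means somewhat fewer mediator events in a very large cohort. Section 9.4 does not mention a present-on-admission flag, so its availability must be confirmed first. The text should also say how ties are handled: if MACE codes from the same stay are dated at admission too, pneumonia dated that day would not precede the censoring date.

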# 9.3.4. Censoring

### Table 4.Censoring Variables

Variable	Role	Operational definition	Measurement period
Outcome under study	Censoring	See outcome table above. Table 2.	Follow-up
Disenrollment	Censoring	The month an individual disenrolls from the insurance plan, as indicated in the Master Beneficiary Summary File. Disenrollment date is calculated as the maximum date of enrollment.	Follow-up
Death	Censoring	Date of death reported in the database.	Follow-up
End of study period	Censoring	December 31, 2019	Follow-up
End of follow-up	Censoring	365 days after the index date for the 1- year analysis and 1095 days after the index date for the 3 year analysis.	Follow-up
PPSV23 receipt	Censoring	1 CPT or NDC code for PPSV23 vaccination during follow-up.	Follow-up
PCV13 receipt	Censoring	1 CPT or NDC code for PCV13 receipt during unvaccinated follow-up.	Follow-up
		1 CPT or NDC code for receipt of a second PCV13 vaccine during vaccinated follow-up.	

PFIZER CONFIDENTIAL

CT24-WI-GL02-RF02 6.0 Non-Interventional Study Protocol Template For Secondary Data Collection Study Page 26 of 53

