### 9. RESEARCH METHODS

#### 9.1. Study Design

This structured secondary data collection study will be a retrospective cohort study using Centers for Medicare and Medicaid Services (CMS) Medicare data to examine the effect of PCV13 receipt on the risk of MACE among adults aged  $\geq 65$  years in the United States. Individuals will be identified using Medicare Fee-for-Service (FFS) Parts A and B enrollment and claims data.

The analysis will be conducted at the time-segment level using a target trial emulation approach. In this time-segment design, individuals who receive a PCV13 vaccine during the study period can contribute up to two time segments during the follow-up period: a PCV13 unvaccinated time segment and a PCV13 vaccinated time segment. Each segment will be attributed to the appropriate vaccination exposure status cohort, resulting in the individual having two separate index dates included in the analysis. Inclusion/exclusion criteria and baseline characteristics will be assessed separately for these two index dates. For PCV13 unvaccinated patients, multiple eligible times may be identified within the study period, but only the first eligible time will be selected due to the large sample size of the unvaccinated cohort. Individuals who remain unvaccinated throughout the entire follow-up period can contribute a maximum of 1 time segment, which will be attributed to the unvaccinated cohort. All analyses will be conducted based on time-segment level data, which allows the exposure variable – PCV13 vaccination – to be treated as time-invariant within each segment.

The index date for the vaccinated cohort is defined as the date of first PCV13 vaccination. For the unvaccinated cohort, the index date is defined as the date of the first available healthcare claim that occurs after the eligibility date (September 14, 2014) and ensures a six-month period of continuous enrollment prior to the index date. Eligible vaccinated and unvaccinated index dates are 1) between September 14, 2014 and November 30, 2019 and 2) after the individual has at least 6 months of continuous enrollment in Medicare FFS Parts A and B. The 6 months of continuous enrollment prior to the index date for each time segment will be used as the baseline period. Baseline covariates, including demographics, preventative care behaviors, and comorbidities will be assessed during this period.

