During PCV13 unvaccinated time segments, unvaccinated individuals will be followed from their unvaccinated index date until experiencing one of the following: 1) the outcome, 2) disenrollment, 3) death, 4) receipt of a PCV13 vaccine, 5) receipt of a PPSV23 vaccine, or 6) the end of the study period. During PCV13 vaccinated time segments, vaccinated individuals will be followed starting 14 days after their first PCV13 vaccination and until experiencing one of the following: 1) the outcome,

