#### PFIZER CONFIDENTIAL

CT24-WI-GL02-RF02 6.0 Non-Interventional Study Protocol Template For Secondary Data Collection Study Page 16 of 53 2) disenrollment, 3) death, 4) receipt of a second PCV13 vaccine, 5) receipt of a PPSV23 vaccine, or 6) the end of the study period.

Rationale: A retrospective cohort study design was selected because the PCV13 vaccine was recommended by the Advisory Committee on Immunization Practices (ACIP) for all adults age  $\geq$ 65 years in the United States in 2014. Data on PCV13 eligible individuals with 3 years of follow-up already exists in the Medicare database, which means that the data does not need to be collected prospectively. Additionally, a retrospective cohort was selected instead of a case control design because 1) major cardiovascular events are not considered a rare outcome and 2) a cohort design establishes the temporal relationship between the exposure and outcome. PCV13-vaccinated and PCV13-unvaccinated were selected as the comparison groups because is the comparison that would allow the study to evaluate the impact of PCV13 receipt on risk of MACE.

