# 9.2.2. Exclusion Criteria

Patients meeting any of the following criteria as of the index date will not have the respective time segment included in the study:

- 1. Evidence of PCV13 vaccination prior to the index date
- 2. Evidence of PPSV23 vaccination in the 365 days prior to the index datea
- 3.  $\geq 1$  diagnosis code for a high-risk condition in the 365 days prior to the index datea
- 4. Evidence of iatrogenic immunosuppression in the 6 months prior to the index date
- 5. Pneumonia diagnosis code in the hospital setting in the 365 days prior to the index datea
- 6. MACE diagnosis code in the hospital, SNF, or LTCF setting in the 365 days prior to the index datea
- 7. Medicare Part C enrollment between September 14, 2014 and the index date
- 8. PCV13 vaccinated individuals with a pneumonia diagnosis code in the hospital setting or a MACE diagnosis code in the hospital, SNF, or LTCF setting in the 13 days after first PCV13 vaccination

a. For adults with  $\geq 6$  months, but less than 365 days of prior continuous enrollment, the exclusion criteria will be evaluated during the continuous enrollment period that the adult has available.

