Follow-up time	Outcome descriptive	Unvaccinated follow-up time is measured from the unvaccinated index date through minimum date of censoring. Vaccinated follow-up time is measured from 14 days after first PCV13 vaccination through the minimum date of censoring. Mean, standard deviation (SD), median (Q1-Q3), minimum, and maximum, will also be summarized for the length of follow-up in each group.	Follow-up

PFIZER CONFIDENTIAL CT24-WI-GL02-RF02 6.0 Non-Interventional Study Protocol Template For Secondary Data Collection Study Page 24 of 53

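### In vaccinated segments, a PPSV23 dose from the PCV13 date through day 13 falls between the exclusion window and the censoring window

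*Protocol*

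**What the plan says.** Section 9.1 sets day 0 of a vaccinated segment: "The index date for the vaccinated cohort is defined as the date of first PCV13 vaccination". It then says that "vaccinated individuals will be followed starting 14 days after their first PCV13 vaccination and until experiencing one of the following", and the list of ending events includes "receipt of a second PCV13 vaccine, 5) receipt of a PPSV23 vaccine, or 6) the end of the study period". Table 2 repeats the day-14 start: "Vaccinated follow-up time is measured from 14 days after first PCV13 vaccination through the minimum date of censoring".

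The rules on vaccine receipt are these:

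- **Exclusion (section 9.2.2).** For PPSV23: "Evidence of PPSV23 vaccination in the 365 days prior to the index date". For PCV13: "Evidence of PCV13 vaccination prior to the index date". Both look back from index.
- **Exclusion 8 (section 9.2.2).** This is the only criterion for the 13 days after PCV13. It concerns hospital pneumonia codes and MACE codes, not vaccine claims.
- **Censoring (Table 4).** For PPSV23: "1 CPT or NDC code for PPSV23 vaccination during follow-up". For a repeat PCV13 dose: "1 CPT or NDC code for receipt of a second PCV13 vaccine during vaccinated follow-up".
- **Covariate (Table 5).** PPSV23 receipt is measured only from 1 to 5 years before index.

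Unvaccinated segments are followed from their index date, and PPSV23 receipt ends them (section 9.1).

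**The concern.** The plan intends the contrast to be PCV13 against no PCV13, with PPSV23 person-time taken out of both arms. In a vaccinated segment the look-back exclusion stops the day before index and censoring starts on day 14. The 14 days in between, day 0 included, have no rule for PPSV23. Someone given both vaccines on the same day, or PPSV23 a week later, would be analysed as a PCV13 recipient with no trace of the second vaccine.

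The gap is one-sided. An unvaccinated person who receives PPSV23 on day 5 is censored on day 5. A vaccinated person who does so is not, and can contribute person-time until 1,095 days after index. If the added vaccine changes MACE risk, that change is credited to PCV13. With a cohort of this size, sampling error is so small that even a slight systematic shift can be comparable with it.

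**Working it through.** **1. Windows in a vaccinated segment, day 0 = first PCV13 date**

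| Rule | Days covered | Reaches PPSV23 on days 0 to 13? |
|---|---|---|
| PPSV23 exclusion (9.2.2) | -365 to -1 | No |
| Exclusion 8 (9.2.2) | the 13 days after PCV13, pneumonia and MACE codes only | No |
| PPSV23 censoring (Table 4) | day 14 onward | No |
| PPSV23 covariate (Table 5) | 1 to 5 years before index | No |

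In an unvaccinated segment follow-up begins on day 0, so censoring takes over where the exclusion ends.

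**2. Size of the shift**

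The documents give no share s of vaccinated segments with PPSV23 on days 0 to 13, so s is an assumption. The hazard multiplier for dual against single vaccination is also an assumption here: it is set to the 0.75 that section 7 cites from a Hong Kong cohort. With a fraction s of the arm at 0.75 times the hazard, the PCV13 hazard ratio is multiplied by about 1 - s(1 - 0.75).

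| s | Multiplier | Shift in log hazard ratio (absolute) | A true 0.85 becomes |
|---|---|---|---|
| 0.5% | 0.9988 | 0.0013 | 0.849 |
| 1% | 0.9975 | 0.0025 | 0.848 |
| 3% | 0.9925 | 0.0075 | 0.844 |
| 5% | 0.9875 | 0.0126 | 0.839 |

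If dual receipt had no effect on MACE beyond PCV13 (multiplier 1), the shift would be zero at every s.

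**3. Comparison with sampling error**

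Inputs: about 25 million eligible people (section 9.2), 39.6% vaccinated, control hazard 0.0507 per year, hazard ratio 0.85 (section 9.5), and the shortened mean follow-up times of 0.75 and 2.25 years in Table 6.

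The control hazard agrees with the plan's own 5-year event probability of 21.2%: 0.6 × (1 - exp(-5 × 0.0507)) + 0.4 × (1 - exp(-5 × 0.0507 × 0.85)) = 0.2119.

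Vaccinated: 0.396 × 25 million = 9.9 million. Unvaccinated: 15.1 million. Vaccinated hazard: 0.85 × 0.0507 = 0.0431. Expected events are n × (1 - exp(-hazard × T)), and the half-width is 1.96 × √(1/d0 + 1/d1).

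| Mean follow-up T | Unvaccinated events d0 | Vaccinated events d1 | 95% half-width, log hazard ratio |
|---|---|---|---|
| 0.75 year | 563,000 | 315,000 | 0.0044 |
| 2.25 years | 1,628,000 | 915,000 | 0.0026 |

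The shift equals the half-width when -ln(1 - 0.25s) = half-width. This gives s of about 1.7% at 0.75 year and about 1.0% at 2.25 years. The half-widths are unweighted; weighting would normally widen them and raise these thresholds.

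**The case against.** The strongest reply is that the protocol uses the word follow-up loosely. Table 1 labels the day-0 PCV13 dose as measured in follow-up, and Table 4 counts the 365 and 1,095 days from the index date. A programmer could therefore take the minimum censoring date over all Table 4 events from index. A PPSV23 claim on day 5 would then leave no time from day 14 onward, and the segment would drop out. Deaths and disenrollments on days 0 to 13 must be handled in some such way, and section 9.7 leaves detailed methodology to the SAP.

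That reading is possible, but nothing in the protocol states it, and it does not sit well with Table 4 read beside the explicit day-14 start. The parallel with death and disenrollment is incomplete: those people cannot be under observation on day 14 under any rule, whereas a PPSV23 recipient can. Eligibility and censoring are fixed in this protocol by numbered criteria and a table, so the windows should meet here. Section 9.8 has two analysts programming independently, which is a further reason to state one rule.

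Four stronger readings should not be drawn:

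- **That the bias always favours PCV13.** The 0.75 concerns sequential dual vaccination against a single pneumococcal vaccine; the protocol does not present it as an estimate for doses given within 13 days of each other. Section 7 says results for the polysaccharide vaccine vary by study and outcome. Section 9.2 raises possible hyporesponsiveness to PCV13 when PPSV23 was given in the year before it. The direction is not settled.
- **That these people stay for the whole follow-up.** A later PPSV23 claim, disenrollment, death or the end of the study period still ends the segment. Only the dose on days 0 to 13 fails to.
- **That a second PCV13 dose in the gap is an equal problem.** The same window is uncovered, but that person is still PCV13-exposed, so the contrast with no PCV13 is not contaminated and the 0.75 does not apply.
- **That unvaccinated segments need a matching exclusion.** They are already censored at receipt. Excluding them on a claim after index would condition on the future and discard valid time at risk.

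**Conclusion.** The gap is real on the text as written: in vaccinated segments, PPSV23 from the PCV13 date through day 13 is neither excluded, censored nor adjusted for, while in unvaccinated segments it censors. The likely effect is small, a multiplier of about 0.999 to 0.988. It rests on an assumed share of 0.5% to 5% and a borrowed hazard ratio of 0.75, and its direction is open. It is comparable with the unweighted 95% half-width only if the share is around 1% to 2% or more. The sample-size table is unaffected. This is an inexpensive correction that carries out the plan's own intent, and no reason to doubt the design as a whole.

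**What to change.** Add to section 9.2.2: exclude vaccinated time segments with a PPSV23 claim from the index date through day 13, both inclusive. The whole window precedes the start of vaccinated follow-up, so no counted person-time is conditioned on a later event. For consistency, treat a second PCV13 claim on a different date in that window the same way. Leave unvaccinated segments unchanged. Carry the line into the SAP, and report how many segments it removes, which would also supply the share that is unknown now.

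The cost is one criterion and a small number of vaccinated segments. Even at an assumed 5%, about 495,000 of 9.9 million vaccinated people would be removed (0.05 × 9.9 million), leaving far more than the largest total size required in Table 6, 36,485.
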